9 STATISTICAL ANALYSIS PLAN

This section outlines the statistical analysis strategy and procedures for the study. If, after the study has begun, changes are made to primary and/or key secondary hypotheses, or the statistical methods related to these hypotheses, then the protocol will be amended (consistent with ICH Guideline E9). Changes to the exploratory or other nonconfirmatory analyses made after the protocol has been finalized, but prior to the conduct of any analysis, will be documented in a sSAP and referenced in the CSR for the study. Posthoc exploratory analyses will be clearly identified in the CSR. The PRO analysis plan will be included in the sSAP. A separate biomarker analysis plan may be provided as appropriate in the sSAP.

9.1 Statistical Analysis Plan Summary

Key elements of the statistical analysis plan are summarized below; the comprehensive plan is provided in Sections 9.2 through 9.12.

Study Design Overview	A randomized, open-label, Phase 3 controlled study of the HIF-2α		
	inhibitor, belzutifan, versus everolimus in participants with advanced		
	renal cell carcinoma after prior therapy		
Treatment Assignment	Participants will be randomly assigned in a 1:1 ratio to receive either		
	belzutifan at 120 mg QD or everolimus at 10 mg QD.		
	Stratification factors are as follows:		
	• IMDC prognostic scores: 0 vs 1-2 vs 3-6		
	• Number of prior VEGF/VEGF receptor targeted therapies for		
	advanced RCC: 1 vs 2-3		
Analysis Populations	Efficacy: ITT		
	Safety: APaT		
Primary Endpoints	• PFS		
	• OS		
Secondary Endpoints	• ORR		
	• DOR		
	PRO assessment		
	 AEs and discontinuations due to AEs 		
Statistical Methods for	The primary hypotheses comparing belzutifan to everolimus with		
Key Efficacy Analyses	respect to PFS and OS will be evaluated using a stratified log-rank test.		
	The hazard ratio will be estimated using a stratified Cox regression		
	model. Event rates over time will be estimated within each treatment		
	group using the Kaplan-Meier method. The stratified Miettinen and		
	Nurminen method with strata weighted by sample size will be used for		
	analysis of ORR.		
Statistical Methods for	For analyses in which 95% CIs will be provided for between-treatment		
Key Safety Analyses	differences in the percentage of participants with events, these analyses		
	will be performed using the Miettinen and Nurminen method		
	[Miettinen, O. and Nurminen, M. 1985].		

14-NOV-2024

Interim Analyses	Two IAs are planned for the study. Results will be reviewed by an external DMC. Details are provided in Section 9.7.		
	CCI		
	• Primary purpose: efficacy analyses for PFS, OS, and ORR. Second IA (IA2):		
	• Primary purpose: efficacy analysis for OS and PFS (final analysis). FA:		
	CCI		
	Primary purpose: efficacy analysis for OS.		
Multiplicity	The overall Type I error rate over the primary and secondary		
	hypotheses is strongly controlled at 2.5% (1-sided), with 0.5% initially		
	allocated to PFS (H1), 1.9% initially allocated to OS (H2) and 0.1%		
	initially allocated to ORR (H3). By using the graphical approach of		
	Maurer and Bretz, if one hypothesis is rejected, the alpha will be		
	shifted to other hypotheses [Maurer, W. and Bretz, F. 2013].		
Sample Size and Power	The planned sample size is approximately 736 participants.		
	There will be ~483 deaths at the final OS analysis. With 483 deaths,		
	the study has ~85.4% power for detecting a HR of 0.75 at an initially		
	assigned 0.019 (1-sided) significance level.		
	It is estimated that there will be ~626 events at the final PFS analysis		
	(ie, the second IA of the study). With 626 PFS events, the study has		
	~96.9% power for detecting a HR of 0.70 at an initially assigned 0.005		
	(1-sided) significance level.		
	Based on all randomized participants, the power of the ORR testing at		
	the allocated α =0.001 is approximately 99.9% to detect a 15-		
	percentage point difference between an underlying 5% response rate in		
	the control arm and a 20% response rate in the experimental arm.		

9.2 Responsibility for Analyses/In-house Blinding

The statistical analysis of the data obtained from this study will be the responsibility of the Clinical Biostatistics department of the Sponsor.

The Sponsor will generate the randomized allocation schedule(s) for study treatment assignment for this protocol, and the randomization will be implemented in IRT.

Although this is an open-label study, analyses or summaries generated by randomized treatment assignment, or actual treatment received will be limited and documented. Further documentation will be provided in the sSAP.

An independent radiologist(s) will perform the central imaging review without knowledge of treatment assignments.

9.3 Hypotheses/Estimation

Objectives and hypotheses of the study are stated in Section 3.

9.4 Analysis Endpoints

9.4.1 Efficacy Endpoints

Primary:

PFS – PFS is defined as the time from randomization to the first documented disease progression based on RECIST 1.1 by BICR or death due to any cause, whichever occurs first.

OS – OS is defined as the time from randomization to death due to any cause.

Secondary:

ORR – ORR is defined as the proportion of participants in the analysis population who have a best overall response of either confirmed CR or PR per RECIST 1.1 as assessed by BICR.

DOR – For participants who demonstrated confirmed CR or PR, DOR is defined as the time from the first documented evidence of confirmed CR or PR until the first documented date of disease progression or death due to any cause, whichever occurs first. Responses and progression will be assessed using RECIST 1.1 by BICR.

9.4.2 Safety Endpoints

A description of safety endpoint assessment is provided in Section 4.2.1.3. Assessments include, but not limited to, the incidence of, causality of, and outcome of AEs/SAEs; and changes in laboratory values.

9.4.3 Patient-reported Outcome Endpoints

As described in Section 4.2.1.4, the following PRO assessments will be evaluated:

- Scores from the EORTC QLQ-C30:
 - Global health status/QoL scale (items 29 and 30)
 - Physical functioning scale (items 1-5)
- Scores from the FKSI-DRS
- Health Utility Scores from the EQ-5D-5L

9.5 Analysis Populations

9.5.1 Efficacy Analysis Population

The ITT population will serve as the population for primary efficacy analysis. All randomized participants will be included in this population. Participants will be included in the treatment arm to which they are randomized. The same population will be used for all efficacy analyses unless otherwise specified in the sSAP.

9.5.2 Safety Analysis Population

The APaT population will be used for the analysis of safety data in this study. The APaT population consists of all randomized participants who received at least 1 dose of study treatment. Participants will be included in the treatment group corresponding to the study treatment they actually received for the analysis of safety data using the APaT population. For most participants this will be the treatment group to which they are randomized. Participants who take incorrect study treatment for the entire treatment period will be included in the treatment group corresponding to the study treatment period will be included in the treatment period will be

At least 1 laboratory or vital sign measurement obtained after at least 1 dose of study treatment is required for inclusion in the analysis of each specific parameter. To assess change from baseline, a baseline measurement is also required.

9.5.3 Patient-reported Outcome Analysis Population

The PRO analyses are based on the PRO FAS population, defined as randomized participants who have at least 1 PRO assessment available and have received at least 1 dose of study treatment.

9.6 Statistical Methods

This section describes the statistical methods that address the primary and secondary objectives. Methods related to exploratory objectives will be described in the sSAP.

9.6.1.1 Progression-free Survival

The nonparametric Kaplan-Meier method will be used to estimate the PFS curve in each treatment group. The treatment difference in PFS will be assessed by the stratified log-rank test. A stratified Cox proportional hazard model with Efron's method of tie handling will be used to assess the magnitude of the treatment difference (ie, the HR) between the treatment arms. The HR and its 95% CI from the stratified Cox model with Efron's method of tie handling and with a single treatment covariate will be reported. The stratification factors used for randomization (Section 6.3.2) will be applied to both the stratified log-rank test and the stratified Cox model.

MK-6482-005-09 FINAL PROTOCOL

9.6.1.2 Overall Survival

The nonparametric Kaplan-Meier method will be used to estimate the survival curves. The treatment difference in survival will be assessed by the stratified log-rank test. A stratified Cox proportional hazard model with Efron's method of tie handling will be used to assess the magnitude of the treatment difference (ie, the HR). The HR and its 95% CI from the stratified Cox model with a single treatment covariate will be reported. The stratification factors used for randomization (Section 6.3.2) will be applied to both the stratified log-rank test and the stratified Cox model. Participants without documented death at the time of analysis will be censored at the date the participant was last known to be alive.

ابار

9.6.1.3 Objective Response Rate

The stratified Miettinen and Nurminen's method will be used for comparison of the ORR between 2 treatment groups. The difference in ORR and its 95% confidence interval from the stratified Miettinen and Nurminen's method with strata weighting by sample size will be reported. The stratification factors used for randomization (see Section 6.3.2) will be applied to the analysis.

9.6.1.4 Duration of Response

If sample size permits, the nonparametric Kaplan-Meier method will be used to estimate the DOR curve in each treatment group; estimates of the percentage of subjects still in response and 95% CIs at specific duration time points will be provided.

9.6.1.5 Analysis Strategy for Key Efficacy Endpoints

A summary of the primary analysis strategy for the key efficacy endpoints is provided in Table 8.

Endpoint/Variable	Statistical Method	Analysis Population	Missing Data Approach	
Primary Hypothesis 1	 	Topulation		
PFS as assessed by BICR	Test: Stratified log-rank test	ITT	Primary censoring rule	
according to RECIST 1.1	Estimation: Stratified Cox		Sensitivity analysis 1	
	model with Efron's tie		Sensitivity analysis 2	
	handling method		(More details are in Table 6)	
Primary Hypothesis 2	Primary Hypothesis 2			
OS	Test: stratified log-rank test	ITT	Censored at last known alive	
	Estimation: stratified Cox model		date	
	with Efron's tie handling method			
Key Secondary Hypothesis 3				
ORR as assessed by	Testing and estimation:	ITT	Participants with missing	
BICR according to	stratified Miettinen and		data are considered	
RECIST 1.1	Nurminen method		nonresponders	
Abbreviations: BICR = blinded independent central review; ITT = intent-to-treat; ORR = objective response rate;				
OS = overall survival; PFS = progression-free survival; RECIST 1.1 = Response Evaluation Criteria in Solid				
Tumors Version 1.1.				
Note: Statistical models are described in further detail in the text. For stratified analyses, the stratification factors used for				
randomization will be used as stratification factors for analysis.				

Table 8	Analysis Strategy for Key Efficacy Endpoints
---------	--

9.6.2 Statistical Methods for Safety Analyses

Safety and tolerability will be assessed by clinical review of all relevant parameters, including AEs, ECG, laboratory tests, and vital signs.

Tier 2 Events

Tier 2 parameters will be assessed via point estimates with 95% CIs provided for differences in the proportion of participants with events using the Miettinen and Nurminen method, an unconditional, asymptotic method [Miettinen, O. and Nurminen, M. 1985].

Membership in Tier 2 requires that at least 10% of participants in any treatment group exhibit the event; all other AEs and predefined limits of change will belong to Tier 3. The threshold

MK-6482-005-09 FINAL PROTOCOL

of at least 10% of participants was chosen for Tier 2 events because the population enrolled in this study is in critical condition and usually experiences various AEs of similar types regardless of treatment; events reported less frequently than 10% of participants would obscure the assessment of the overall safety profile and add little to the interpretation of potentially meaningful treatment differences. In addition, Grade 3 to 5 AEs (\geq 5% of participants in 1 of the treatment groups) and SAEs (\geq 5% of participants in 1 of the treatment groups) will be considered Tier 2 endpoints. Because many 95% CIs may be provided without adjustment for multiplicity, the CIs should be regarded as a helpful descriptive measure to be used in safety review, not as a formal method for assessing the statistical significance of the between-group differences.

Tier 3 Events

Safety endpoints that are not Tier 1 or 2 events are considered Tier 3 events. Only point estimates by treatment group are provided for Tier 3 safety parameters.

Continuous Safety Measures

Continuous measures such as changes from baseline in laboratory parameters, summary statistics for baseline, on-treatment, and change from baseline values will be provided by treatment group in table format.

Safety Tier	Safety Endpoint	95% CI for Treatment Comparison	Descriptive Statistics
Tier 2	Any AE ($\geq 10\%$ of participants in one of the treatment groups)	X	X
	Any serious AE (\geq 5% of participants in one of the treatment groups)	X	X
	Any Grade 3 to 5 AE (\geq 5% of participants in one of the treatment groups)	X	X
Tier 3	AEs, Specific AEs, SOCs		Х
	Discontinuation due to AE		X
	Dose interruption due to AE		X
	Change from baseline results (laboratory, ECGs, Vital Signs)		X
Abbreviat	ions: AE = adverse event; SOC = system organ class; X = result	s will be provided.	

 Table 9
 Analysis Strategy for Safety Parameters

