1 PROTOCOL SUMMARY

1.1 Synopsis

Protocol Title: An Open-label, Randomized Phase 3 Study of MK-6482 Versus Everolimus in Participants with Advanced Renal Cell Carcinoma That Has Progressed After Prior PD-1/L1 and VEGF-Targeted Therapies

Short Title: An Open-label, Randomized Phase 3 Study of Belzutifan Versus Everolimus in Participants With Advanced Renal Cell Carcinoma After Prior Therapy

Acronym: MK-6482-005

Hypotheses, Objectives, and Endpoints:

This study will be conducted in male and female participants with advanced clear cell RCC.

Primary Objectives	Primary Endpoints					
To compare belzutifan to everolimus with respect to PFS per RECIST 1.1 as assessed by BICR. Hypothesis (H1): Belzutifan is superior to everolimus with respect to PFS per RECIST 1.1 by BICR.	PFS: the time from randomization to the first documented disease progression or death due to any cause, whichever occurs first					
Objective: To compare belzutifan to everolimus with respect to OS. Hypothesis (H2): Belzutifan is superior to everolimus with respect to OS.	OS: the time from randomization to death due to any cause					
Secondary Objectives	Secondary Endpoints					
Objective: To compare belzutifan to everolimus with respect to ORR based on RECIST 1.1 as assessed by BICR. Hypothesis (H3): Belzutifan increases ORR according to RECIST 1.1 by BICR compared to everolimus.	OR: CR or PR					
Objective: To evaluate the DOR as assessed by BICR according to RECIST 1.1.	DOR: the time from first documented evidence of CR or PR until either disease progression or death due to any cause, whichever occurs first					
Objective: To evaluate the safety and tolerability of belzutifan compared to everolimus.	 AEs Study intervention discontinuation due to AEs 					

Objective: To evaluate TTD and change from baseline in HRQoL using the EORTC QLQ-C30 and the FKSI-DRS.	 PRO scores for the following domains: EORTC QLQ-C30 global health status/HRQoL (Items 29 and 30) 				
	• EORTC QLQ-C30 physical functioning (Items 1-5)				
	• FKSI-DRS Subscale (Items 1-9)				
Objective: To characterize health utility as measured using the EuroQoL EQ-5D-5L.	Health utility scores from the EQ-5D-5L				

Overall Design:

Study Phase	Phase 3				
Primary Purpose	Treatment				
Indication	Renal cell carcinoma				
Population	Participants with unresectable, locally advanced, or metastatic RCC after prior therapy				
Study Type	Interventional				
Intervention Model	Parallel				
	This is a multisite study.				

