3 HYPOTHESES, OBJECTIVES, AND ENDPOINTS

This study will be conducted in male and female participants with advanced clear cell RCC.

Primary Objectives	Primary Endpoints
To compare belzutifan to everolimus with respect to PFS per RECIST 1.1 as assessed by BICR. Hypothesis (H1): Belzutifan is superior to everolimus with respect to PFS per RECIST 1.1 by BICR.	PFS: the time from randomization to the first documented disease progression or death due to any cause, whichever occurs first
Objective: To compare belzutifan to everolimus with respect to OS. Hypothesis (H2): Belzutifan is superior to everolimus with respect to OS.	OS: the time from randomization to death due to any cause
Secondary Objectives	Secondary Endpoints
Objective: To compare belzutifan to everolimus with respect to ORR based on RECIST 1.1 as assessed by BICR. Hypothesis (H3): Belzutifan increases ORR	OR: CR or PR
according to RECIST 1.1 by BICR compared to everolimus.	
Objective: To evaluate the DOR as assessed by BICR according to RECIST 1.1.	DOR: the time from first documented evidence of CR or PR until either disease progression or death due to any cause, whichever occurs first
Objective: To evaluate the safety and	• AEs
tolerability of belzutifan compared to everolimus.	• Study intervention discontinuation due to AEs
Objective: To evaluate TTD and change	PRO scores for the following domains:
trom baseline in HRQoL using the EORTC QLQ-C30 and the FKSI-DRS.	• EORTC QLQ-C30 global health status/HRQoL (Items 29 and 30)
	• EORTC QLQ-C30 physical functioning (Items 1-5)
	• FKSI-DRS Subscale (Items 1-9)
Objective: To characterize health utility as measured using the EuroQoL EQ-5D-5L.	Health utility scores from the EQ-5D-5L

Tertiary/Exploratory Objectives	Tertiary/Exploratory Endpoints

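### Discontinuation due to AEs is a named secondary endpoint under a comparative safety objective, but the plan gives it one percentage per arm and no between-arm difference or CI

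*Protocol*

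**What the plan says.** The secondary safety objective (Protocol Synopsis 1.1, repeated in Section 3) is "To evaluate the safety and tolerability of belzutifan compared to everolimus". SAP Section 3.3.2 states the same objective under the drug's code name. Protocol Section 3 lists two endpoints for it: AEs, and "Study intervention discontinuation due to AEs". The analysis summaries (Protocol 9.1, SAP 3.1) carry both among the secondary endpoints, as "AEs and discontinuations due to AEs".

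Safety outputs are assigned by tier (Protocol 9.6.2, SAP 3.6.2). SAP 3.6.2 says that this trial has no Tier 1 events.

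- **Tier 2:** "Tier 2 parameters will be assessed via point estimates with 95% CIs provided for differences in the proportion of participants with events", by the Miettinen-Nurminen method. For AEs, "Membership in Tier 2 requires that at least 10% of participants in any treatment group exhibit the event". Serious AEs and Grade 3 to 5 AEs enter at 5%.
- **Tier 3:** "Only point estimates by treatment group are provided for Tier 3 safety parameters".

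Protocol Table 9 lists "Discontinuation due to AE" under Tier 3. The row is marked for descriptive statistics and left blank in the column for a treatment-comparison CI. SAP Table 4 also lists it under Tier 3.

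**The concern.** The objective is worded as one drug relative to the other, and discontinuation due to AEs is one of only two endpoints attached to it. An individual AE term that reaches 10% gets an estimated difference with its precision, although no single term is a named endpoint. Discontinuation, which is named, gets neither.

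The PRO endpoints make the contrast plainer. Their objective is only to evaluate, with no comparator in the wording, yet SAP 3.6.3.3 and 3.6.3.4 plan between-arm differences or hazard ratios with 95% CIs.

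What is at stake is modest. Followed as written, the report would show two percentages and leave the reader to work out the difference and its uncertainty.

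**Working it through.** The plan states no figure for this endpoint, so there is none to reproduce. The check is a comparison of the text, followed by an illustration of precision.

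**1. Is the endpoint named under a comparative objective?** Yes: Protocol 1.1 and 3, repeated in the 9.1 and SAP 3.1 summaries.

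**2. Which tier is it in?** Tier 3, in Protocol Table 9 and SAP Table 4.

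**3. Could its frequency move it to Tier 2?** Not as written. The 10% rule classifies AEs and predefined limits of change. Table 9 also lists AEs and specific AEs in Tier 3, but these have Tier 2 rows that take over once a threshold is met. The discontinuation row has no Tier 2 counterpart and no frequency condition.

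**4. Is a comparison planned elsewhere?** No difference, CI or time-to-event comparison for discontinuation due to AEs appears in either document.

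**5. How precise would the interval be?** Inputs: about 368 per arm (Protocol 4.1) and assumed rates of 5% to 20%. A simple approximation with equal rates p is

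half-width = 1.96 × √(2p(1 − p)/368)

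- p = 5%: 1.96 × √(2 × 0.0475/368) = 1.96 × 0.0161 = 3.1 points
- p = 20%: 1.96 × √(2 × 0.16/368) = 1.96 × 0.0295 = 5.8 points

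The Miettinen-Nurminen score interval, which is the plan's own method (unstratified here, with event counts rounded to whole participants), gives:

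| Belzutifan | Everolimus | Difference (points) | 95% CI |
|---|---|---|---|
| 5% | 5% | 0.0 | −3.2 to 3.2 |
| 10% | 10% | 0.0 | −4.4 to 4.4 |
| 15% | 15% | 0.0 | −5.2 to 5.2 |
| 20% | 20% | 0.0 | −5.8 to 5.8 |
| 5% | 10% | −5.2 | −9.1 to −1.4 |
| 10% | 15% | −4.9 | −9.7 to −0.1 |
| 5% | 15% | −10.1 | −14.5 to −5.9 |

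The half-width runs from about 3 to 6 points. The figure of 368 counts randomized participants, whereas the safety population (APaT, Protocol 9.5.2) requires at least one dose. Any participants never dosed would widen the intervals slightly, in proportion to 1/√n.

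**The case against.** The strongest reply is that nothing is broken. The PFS, OS and ORR objectives are worded as comparisons and each has a hypothesis. The safety objective is to evaluate, has no hypothesis, and Protocol 9.6.2 says that safety will be assessed by clinical review. Side-by-side percentages from randomized arms are already a descriptive comparison, and anyone can compute an interval from them. This stands to a large extent: neither document promises a CI for every safety endpoint. It makes the point an improvement rather than an error.

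A second reply is that a crude difference in proportions could look more informative than it is.

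- Belzutifan follows the protocol's own rules for permanent discontinuation (Table 3), while everolimus follows its package insert (6.6.2).
- Investigators know the assignment (6.3.3).
- Treatment continues to progression, so exposure would be longer on belzutifan if the assumed PFS hazard ratio of 0.7 holds.

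All of this stands, and the limits should be stated beside the interval. They apply equally to the two bare percentages.

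A third reply cites the plan's reason for its 10% threshold, that rarer events add little to the interpretation. That reason concerns many infrequent AE terms crowding the tables. It does not reach one summary endpoint fixed in advance.

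Three stronger readings might be inferred and are not supported:

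- **That tolerability goes unestimated, or that this is its only endpoint.** AEs are the other named endpoint, those meeting the Tier 2 thresholds get CIs, and dose interruption due to AE is tabulated.
- **That the interval would settle whether the arms differ.** Protocol 9.6.2 says these CIs are descriptive and not a formal way to judge significance, so whether one includes zero is not the argument.
- **That discontinuation is a better measure of tolerability than individual AE terms.** The documents do not establish this, and the point does not need it.

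**Conclusion.** The point holds as a minor one. For a named secondary endpoint under an objective that refers to the comparator, the plan fixes an output without a between-arm estimate or its precision. It supplies both for AE terms that merely reach a frequency threshold. This is a stated rule, not an omitted detail.

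The missing interval would have a half-width of about 3 to 6 percentage points. That rests on about 368 participants per arm and on assumed discontinuation rates of 5% to 20%. The finding itself rests only on the text. A reader might go further and infer a missing hypothesis test or a type I error problem. The documents support neither: the endpoint has no hypothesis and lies outside the alpha allocation. Sample size, power and the primary conclusions are unaffected.

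**What to change.** In Protocol Table 9 and SAP Table 4, mark the row for discontinuation due to AE for a between-arm difference with a Miettinen-Nurminen 95% CI in the APaT population, whatever its observed frequency. Label it descriptive and unadjusted for multiplicity, like the Tier 2 intervals. Add a note that the crude difference does not account for unequal treatment duration, open-label assignment or the different discontinuation rules in the two arms.

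Protocol Section 9 lets nonconfirmatory changes made before any analysis be documented in the supplemental SAP. If analyses have already been run, the addition should be identified as post hoc in the CSR.

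The cost is one table row in each document and one more interval from a method already specified, with no new data. The downside is small: one further unadjusted interval, and the risk that a crude difference is over-read, which the note is there to limit.
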